3. Medical history of HF with at least 1 prior hospitalization for HF (not due to arrhythmia or a conduction system disturbance treated with a permanent pacemaker) **OR** clinical evidence of HF (with or without hospitalization) manifested by signs and symptoms of volume overload or elevated intracardiac pressures (eg, elevated jugular venous pressure, shortness of breath or signs of pulmonary congestion on x-ray or auscultation, peripheral edema) that currently requires treatment with a diuretic.
4. Patient meets one of the following criteria:
 - a. Tafamidis naïve; in addition to patients who have never taken tafamidis, those who have been on tafamidis for ≤30 days total and have not received any tafamidis in the 6 months prior to baseline will be considered tafamidis naïve and may qualify for the study.
 - b. Currently on tafamidis (for ≥6 months) and has demonstrated disease progression, as determined by the Investigator. (At the time of study entry, tafamidis treatment must be on-label use of commercial tafamidis.)
5. Patient is clinically stable, with no CV-related hospitalizations within 6 weeks prior to randomization, as assessed by the Investigator.
6. Able to complete ≥150 m on the 6-MWT at screening.
7. Screening NT-proBNP >600 ng/L and <8500 ng/L.

Informed Consent

8. Patient is able to understand and is willing and able to comply with the study requirements and to provide written informed consent; and patient agrees to sign the medical records release form for collection of vital status.

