6.2.5.1. Cardiac Biomarkers

The cardiac biomarkers NT-proBNP and troponin I will be used to assess cardiac stress and heart failure severity. These biomarkers have been shown to be prognostic of outcomes in HF, including in ATTR amyloidosis.[[Damy 2016](#); [Kristen 2017](#); [Merlini 2016](#)] Blood samples will be drawn to measure cardiac biomarker levels at the timepoints specified in the Schedule of Assessments ([Table 1](#) and [Table 2](#)) and will be measured at a central laboratory. At screening Visit 1, only NT-proBNP will be assessed for eligibility purposes.

Details on cardiac biomarker sample collection, processing, and storage will be provided in a Study Laboratory Manual.

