7.2.5.1. Primary Endpoint

The primary endpoint, change from baseline at Month 12 in the 6-MWT, will be analyzed using a mixed-effects model repeated measures (MMRM) approach. The outcome variable is change

from baseline in the 6-MWT. The model will include the baseline value as a covariate, treatment, visit, the treatment-by-visit interaction, baseline tafamidis (yes vs no), genotype (hATTR vs wtATTR), and age (<75 vs \geq 75 years) as fixed factors, and patient as a random effect. The primary comparison is the contrast (difference in least squares [LS] means) between the patisiran and placebo groups at Month 12.

Sensitivity analyses will be detailed in the SAP.

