7.2.5.2. Secondary Endpoints

Secondary endpoints are described in Section 2.

KCCQ-OS will be analyzed using a similar MMRM model as used for the primary endpoint.

The composite endpoint of all-cause mortality, frequency of CV-related hospitalizations and change from baseline in 6-MWT will be analyzed using a generalized rank-based win ratio method, which makes pairwise comparisons (for all possible patisiran/placebo patient pairs) of the 3 components in the hierarchical order specified above. The point estimate for the win ratio is defined as the total number of better outcomes divided by the total number of worse outcomes in the patisiran group. The detailed algorithm for assessment of this endpoint will be provided in the SAP.

The composite endpoint of all-cause mortality and all-cause hospitalizations will be analyzed using an Andersen-Gill model stratified by baseline tafamidis (yes vs no), including treatment, genotype (hATTR vs wtATTR), NYHA Class (I/II vs III), and age (<75 vs \geq 75 years) as covariates.

Patients who undergo a heart transplantation and/or ventricular assist device placement after randomization will be handled in the same manner as death in the primary analyses of mortality related endpoints.

To control the overall Type I error rate, secondary endpoints will be tested in a prespecified hierarchical order.

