- Removing reference to steroid doses the night before IV infusion as these references were included in error.
- Adding guidance to allowing for local TTR genotype testing if results are not available at Screening.
- Increasing the possible number of patients to be included in the subset who will have technetium scintigraphy during the study as an optional exploratory imaging assessment.
- Clarifying that follicle-stimulating hormone testing will be performed in all post-menopausal women to confirm suspected post-menopausal status.
- Broadening rescreening criteria to allow more flexibility.
- Clarifying that DNA will not be collected as biological samples for potential exploratory investigations.
- Removing baseline NYHA from the mixed-effects model repeated measures (MMRM) for the primary analysis to create a more parsimonious model.

A detailed summary of changes is provided in [Table 1](#). Minor changes such as corrections to typographical errors, punctuation, grammar, abbreviations, and formatting (including administrative changes between the original protocol and this amendment) are not detailed.

Table 1: Protocol Amendment 1 – Detailed Summary of Changes

The primary section(s) of the protocol affected by the changes in Protocol Amendment 1 are indicated. The corresponding text has been revised throughout the protocol. Deleted text is indicated by ~~strikeout~~; added text is indicated by **bold** font.

Purpose: Clarified study visit window for Week 3 (Day 22) is ± 3 as this was left out in error; added a window for randomization based on questions from sites.

The primary change occurs in Table 1: Schedule of Assessments – Double-blind Period (Screening to Month 12 Efficacy Assessments).

Study Day \pm Visit Window column header above Week 3 now reads: D22 \pm 3

The cell in the randomization row under the details column now reads: 3.5 **Window: 5D prior to Day 1**

Purpose: Added ursodeoxycholic acid to the list of prohibited medications as it is commonly prescribed for the same reasons as tauroursodeoxycholic acid which is already prohibited.

The primary change occurs in Section 4.2, Exclusion Criterion 10

Now reads:

10. Is currently taking doxycycline, **ursodeoxycholic acid**, or tauroursodeoxycholic acid; if previously on any of these agents, must have completed a 30-day wash-out prior to dosing (Day 1).

Section(s) also containing this change:

- 5.3. Concomitant Medications and Procedures

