Purpose: Based on feedback from a competent authority, removed text so Investigators will be able to decide whether a dose can be considered an overdose without consulting the Sponsor. In addition added language referencing the Pharmacy Manual for dose recording and reporting requirements.

The primary change occurs in Section 6.5.7.8. Overdose Reporting.

An overdose is defined as any dose administered to or taken by a patient (accidentally or intentionally) that exceeds the highest daily dose, or is at a higher frequency, than included in the protocol. ~~The Investigator will decide whether a dose is to be considered an overdose, in consultation with the Sponsor.~~ In the event of an overdose, the actual dose administered must be recorded ~~in the eCRF as specified in the Pharmacy Manual.~~

All reports of overdose (with or without an AE) must be reported within 24 hours ~~to the Sponsor or designee following the instructions outlined in the Pharmacy Manual for reporting an overdose.~~

Purpose: Clarified that DNA will not be collected as biological samples for potential exploratory investigations.

The primary change occurs in Section 6.6, Biomarkers and Biospecimen Repository.

Now reads: Biological specimens will be collected at the intervals indicated in the Schedule of Assessments (Table 1 and Table 2). Potential exploratory investigations may include DNA, RNA, or biochemical metabolite assessments as they relate to disease progression, efficacy or safety.

Purpose: For the primary analysis of 6-MWT, the MMRM model previously specified in the protocol included baseline NYHA class as a factor. Baseline NYHA class is associated with disease severity, however, it correlates with baseline 6-MWT which is included as a continuous covariate in the model. In the protocol amendment, baseline NYHA class has been removed from the MMRM in order to create a more parsimonious model.

The primary change occurs in 7.2.5.1, Primary Endpoint

The model description now reads: The model will include the baseline value as a covariate, treatment, visit, the treatment-by-visit interaction, baseline tafamidis (yes vs no), genotype (hATTR vs wtATTR), ~~NYHA Class (I/II vs III)~~, and age (<75 vs \geq 75 years) as fixed factors, and patient as a random effect.

Section(s) also containing this change:

- Synopsis

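### The primary 6-MWT model leaves out NT-proBNP, a prognostic marker known for every eligible patient before randomisation: a missed efficiency, not an error

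*Protocol*

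**What the plan says.** Section 7.2.5.1 fixes the primary model term by term: "The model will include the baseline value as a covariate, treatment, visit, the treatment-by-visit interaction", then baseline tafamidis, genotype and age below or from 75 years, "as fixed factors, and patient as a random effect". Only the sensitivity analyses are passed to the SAP there. NYHA class, NT-proBNP, eGFR and ATTR stage are not in the list. For the first secondary endpoint, Section 7.2.5.2 says: "KCCQ-OS will be analyzed using a similar MMRM model as used for the primary endpoint".

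NYHA class was in the model of the April 2019 protocol. The Amendment 1 summary of changes records "Removing baseline NYHA from the mixed-effects model repeated measures (MMRM) for the primary analysis to create a more parsimonious model", and gives as the reason that "it correlates with baseline 6-MWT which is included as a continuous covariate in the model". It does not discuss NT-proBNP. NYHA class remains in the third randomisation stratum, combined with age (Section 3.5), and in the Andersen-Gill model for mortality and hospitalisation (Section 7.2.5.2).

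NT-proBNP is inclusion criterion 7 in Section 4.1: "Screening NT-proBNP >600 ng/L and <8500 ng/L". Amendment 2 lowers the lower limit to 300 ng/L except in permanent or persistent atrial fibrillation. Section 6.2.5.1 places the measurement before randomisation ("At screening Visit 1, only NT-proBNP will be assessed for eligibility purposes"), in a central laboratory, and says of NT-proBNP and troponin I: "These biomarkers have been shown to be prognostic of outcomes in HF, including in ATTR amyloidosis".

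The sections quoted are the Amendment 1 protocol. The Amendment 2 summary shows a change to Section 7.2.5.2 but none to Section 7.2.5.1. The Amendment 2 body is not in the text at hand, so it cannot be confirmed directly that this model is still current.

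**The concern.** The only measure of disease severity in the primary model is the baseline walk. NT-proBNP is a different kind of measurement, is already collected, and spans a wide range among eligible patients: 8500/600 is about 14-fold, and 8500/300 is about 28-fold under Amendment 2. The reason given for dropping NYHA class, overlap with the walk, was not examined for NT-proBNP, and nothing took the place of NYHA class.

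Two things could be gained. The first is precision: a baseline covariate that explains part of the 12-month change lowers the standard error of the treatment difference. The primary test also opens the fixed testing sequence in Section 7.2.5, so every secondary endpoint depends on it.

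The second is the missing-data assumption. Walks after tafamidis drop-in are censored in the primary analysis, drop-in follows the investigator's medical judgement (Section 5.3.1), and patients who die have no Month 12 walk. Both kinds of loss plausibly track severity. The MMRM can allow for this only through the covariates and earlier walks it contains.

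**Working it through.** **1. The plan's own figure.** Inputs from Section 7.1: 33 m in tafamidis-naïve patients (70%), 20 m in those on baseline tafamidis (30%), SD 75 m, 300 patients, two-sided alpha 0.05. Section 3.5 gives 1:1 allocation, so 150 per arm.

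- Weighted difference: 0.7 × 33 + 0.3 × 20 = 29.1 m. The plan uses about 29 m.
- SE = 75 × √(2/150) = 8.66 m.
- Power = Φ(29/8.66 − 1.96) = 91.8% (91.6% with the noncentral t).
- 90% power needs 282 patients, so 300 leaves 18 spare.

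The stated power above 90% therefore reproduces.

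**2. Gain in precision.** Let r be the partial correlation of baseline log NT-proBNP with Month 12 walk change, given the terms already in the model. The documents give no value, so r is assumed. Taking 75 m as the residual SD of the present model, the SD becomes 75 × √(1 − r²), and the sample size of equal worth is 300/(1 − r²).

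| r (assumed) | Variance reduction | SD (m) | SE (m) | Power | Equivalent n |
|---|---|---|---|---|---|
| 0 | 0% | 75.0 | 8.66 | 91.8% | 300 |
| 0.1 | 1% | 74.6 | 8.62 | 92.0% | 303 |
| 0.2 | 4% | 73.5 | 8.49 | 92.8% | 312.5 |
| 0.3 | 9% | 71.5 | 8.26 | 94.0% | 330 |
| 0.4 | 16% | 68.7 | 7.94 | 95.5% | 357 |

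The working range is 0.1 to 0.3; the row for 0.4 shows the trend beyond it. At r = 0 the cost is about one degree of freedom.

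**3. With loss of walks.** The protocol states no loss rate. If 20% is assumed, with nothing recovered from earlier visits (120 per arm), power is 85.0% without the marker and 85.3%, 86.4%, 88.1% and 90.5% at r = 0.1, 0.2, 0.3 and 0.4.

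**4. Missing-at-random.** Simulation with 1,500 runs per scenario and 300 patients: walk change at two visits (SD 55 and 75 m, correlation 0.6), true Month 12 difference 29 m, about 20% missing at Month 12. The estimator is the likelihood estimate that an MMRM gives under monotone missingness. All missingness inputs are assumed. The SD of the estimates is about 9 m, so the simulation error of a mean is about 9/√1500 = 0.23 m.

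- Missingness depends on the marker equally in both arms: the mean error stays within 0.3 m with or without the marker, so no bias is visible.
- Only placebo missingness depends on the marker: leaving it out gives −0.5, −1.2, −1.5 and −2.1 m at r = 0.1, 0.2, 0.3 and 0.4. Including it brings the error to within 0.2 m.

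**The case against.** The strongest reply is that this is a modelling preference. The covariate set was considered in Amendment 1, the test is valid, and the stated power is correct. All of that stands, and it is why the point is an optional improvement. It does not answer why a marker already collected should be left out, because the parsimony argument was made for NYHA class alone.

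- **Unknown correlation.** Being prognostic of heart failure outcomes does not show that NT-proBNP predicts walk change beyond the baseline walk. A reader might infer a guaranteed gain in precision; the documents do not support that. At 0.1 to 0.2 the gain is negligible, and it becomes useful from about 0.3.
- **Which SD is 75 m?** Section 7.1 does not say whether it is raw or residual. If it is raw and the present covariates explain an assumed 10% of variance, the SE is 8.66 × √0.9 = 8.22 m and power is already about 94%. A reader might infer from the 18 spare patients that the trial is short of power; that does not follow.
- **Missing data.** A reader might infer that the primary estimate is biased. The simulation shows bias only when missingness depends on severity differently by arm, and in the pattern tried it lowered the apparent benefit. Handling of missing data is left to the SAP, which is no fault of the protocol. Nor does a covariate settle how deaths should be treated.
- **KCCQ-OS.** A reader might say that this model also has no severity measure besides the walk. It would presumably carry baseline KCCQ-OS, a heart failure health-status score, so that reading fails.
- **Atrial fibrillation.** The Amendment 2 summary notes that fibrillation itself raises NT-proBNP, so the term mixes rhythm with severity. That may limit what it explains; it does not make adjustment harmful.

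**Conclusion.** The point holds as a missed efficiency. The primary 6-MWT model adjusts for no cardiac biomarker, although NT-proBNP is known for every eligible patient before randomisation and the protocol itself calls it prognostic. The planned analysis is not wrong, and its sample size is adequate on its own inputs.

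The size is small to modest: 1% to 9% less variance, power of about 92% to 94% against 91.8%, worth about 3 to 30 patients. This rests on an assumed partial correlation of 0.1 to 0.3 and on reading 75 m as a residual SD. The benefit for missing-at-random is real in direction, but it affects the treatment contrast mainly under arm-specific dependence on severity, which the documents neither show nor exclude. The conclusion also assumes that Section 7.2.5.1 was carried unchanged into Amendment 2.

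**What to change.** Before unblinding, prespecify baseline log NT-proBNP as one continuous covariate in the 6-MWT MMRM. Use the screening value if the Day 1 value is missing, so that no patient leaves the model for want of the covariate. Add the same term to the KCCQ-OS model, alongside the baseline KCCQ-OS that it presumably already contains.

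The cost is one line in the protocol or SAP, about one degree of freedom and no new data. The model becomes slightly less parsimonious than the one chosen in Amendment 1, and the coefficient will partly reflect atrial fibrillation as well as severity, so it should not be interpreted as a pure severity effect. If the sponsor prefers to keep the present model, the lesser step is a named sensitivity analysis with the term, or a sentence saying why it is left out.

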The primary endpoint, change from baseline at Month 12 in the 6-MWT, will be analyzed using a mixed-effects model repeated measures (MMRM) approach. The outcome variable is change from baseline in the 6-MWT. The model will include the baseline value as a covariate, treatment, visit, the treatment-by-visit interaction, baseline tafamidis (yes vs no), genotype (hATTR vs wtATTR), and age (<75 vs ≥ 75 years) as fixed factors, and patient as a random

effect. The primary comparison is the contrast (difference in least squares [LS] means) between the patisiran and placebo groups at Month 12.

To control the overall Type I error rate, secondary endpoints will be tested in a prespecified hierarchical order.

For patients who are tafamidis treatment-naïve at baseline and start tafamidis during the double-blind period, the primary analysis of the primary endpoint will censor data collected after the initiation of tafamidis treatment post-randomization.

Safety data will be summarized descriptively.

Figure 1: Study Design

[figure not shown]

Table 1: Schedule of Assessments – Double-blind Period (Screening to Month 12 Efficacy Assessments)

Table 1: Schedule of Assessments – Double-blind Period (Screening to Month 12 Efficacy Assessments)

Table 1: Schedule of Assessments – Double-blind Period (Screening to Month 12 Efficacy Assessments)

Abbreviations: AE=adverse event; ADA=antidrug antibodies; Con Meds=concomitant medications; CMR=cardiac magnetic resonance; D=day; Disc=discontinuation; ECG=electrocardiogram; FSH=follicle-stimulating hormone; KCCQ=Kansas City Cardiomyopathy Questionnaire; M=month;

mBMI=modified body mass index; 6-MWT=6-minute walk test; NA=not applicable; NT-proBNP=N-terminal prohormone B-type natriuretic peptide; NYHA=New York Heart Association; PK=pharmacokinetics; PND=Polyneuropathy Disability; QoL-DN=Quality of Life-Diabetic Neuropathy; TTR=transthyretin; V=visits.

^a This efficacy visit is conducted 7 to 14 days after the prior visit.

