A 1.5-month window will be used to group 6-MWT assessments to the Month 6 (Weeks 25-26), Month 9 (Weeks 37-38), and Month 12 (Weeks 52-53) visits. During the double-blind period, a patient may opt to begin tafamidis treatment or to discontinue study treatment, in which case they would complete a Pre-tafamidis Drop-in Visit ([Table 1](#)) or Early Treatment Discontinuation Visit ([Table 2](#)), respectively. To avoid the potential training effect from repeated assessments of the 6-MWT within a short period of time, only one 6-MWT assessment should be collected for the following time periods: Day 2 to Day 214 (for Month 6), Day 215 to Day 319 (for Month 9), and Day 320 to Day 372 (for Month 12).

Within a given time period, the 6-MWT assessment should be performed at whichever visit occurs first (scheduled assessment, Pre-tafamidis Drop-in Visit, or Early Treatment Discontinuation Visit); no additional 6-MWT assessments should be made in that time period. In later time periods, the 6-MWT should be assessed per the Schedule of Assessments ([Table 1](#)).

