7.1. Determination of Sample Size

The planned enrollment for this study is 300 patients. For the change from baseline at Month 12 in the 6-MWT, assuming a treatment difference of 33 meters between patisiran and placebo in the treatment-naïve group and 20 meters in patients with baseline tafamidis, the weighted average treatment difference between patisiran and placebo in the overall population is approximately 29 meters (standard deviation = 75 meters) assuming 70% are in the treatment-naïve group and 30% are in the baseline tafamidis group. A sample size of 300 patients provides >90% power for a 2-sided test to detect a mean difference between treatment groups at a 2-sided alpha = 0.05. Additional patients may be enrolled based on a recommendation to increase the sample size in the interim assessment ([Section 7.2.10](#)).

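### The primary MMRM names only a random patient effect; read literally this pools variance over Months 6, 9 and 12, which makes the Month 12 test anti-conservative if 6-MWT change becomes more variable over time

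*Protocol*

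**What the plan says.** Section 7.2.5.1 and the synopsis state that the change from baseline in 6-MWT is "analyzed using a mixed-effects model repeated measures (MMRM) approach". The model contains baseline value, treatment, visit, treatment-by-visit, baseline tafamidis, genotype and age, with the categorical terms "as fixed factors, and patient as a random effect". The test is the difference in LS means "between the patisiran and placebo groups at Month 12". Nothing is said about the residual covariance: neither a structure nor a statement that the variance is common to all visits.

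Three post-baseline visits enter the model. Section 6.2.1 says: "A 1.5-month window will be used to group 6-MWT assessments to the Month 6 (Weeks 25-26), Month 9 (Weeks 37-38), and Month 12 (Weeks 52-53)". For the first secondary endpoint, section 7.2.5.2 says: "KCCQ-OS will be analyzed using a similar MMRM model as used for the primary endpoint".

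The opening of section 7 leaves implementation to the SAP, but ties the SAP to the principal features of the protocol. The only SD in the document is 75 m for change at Month 12 (section 7.1).

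This text is from the Amendment 1 protocol body. Amendment 1 edited the model sentence to remove NYHA class and left the patient term in place. The Amendment 2 summary of changes lists no change to the model; the Amendment 2 body is not shown.

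**The concern.** A single random patient intercept with independent residuals of equal variance implies one variance at every visit and one correlation for every pair of visits. The primary question concerns Month 12 alone, yet its standard error would then be built from all three visits. If change from baseline is less variable at Months 6 and 9 than at Month 12, the pooled figure is too small for Month 12.

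Rising variability is plausible here, though not documented. Section 1.4 describes a steady decline in 6-MWT in this disease. The population mixes two genotypes and two tafamidis strata with different assumed effects. The Month 6 bin in section 6.2.1 runs from Day 2 to Day 214 and takes the first eligible visit, so some values measured soon after baseline can enter as Month 6.

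The primary test opens the testing sequence for all secondary endpoints, so an error in its size passes down the line. Some Month 12 values will also be missing for the primary analysis, because section 7.2.5 censors data after tafamidis drop-in. The assumed covariance then also governs how earlier visits inform the Month 12 estimate.

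**Working it through.** **Inputs from the protocol.** 300 patients randomized 1:1, so 150 per arm; SD 75 m at Month 12; differences of 33 m (70% tafamidis-naïve) and 20 m (30% on tafamidis); two-sided alpha 0.05; visits at Months 6, 9 and 12.

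**Inputs assumed.** SDs of change at Months 6 and 9. The SD of 75 m is taken as the residual SD, with no allowance for covariate adjustment.

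**The plan's own figure.** The weighted difference is 0.7 × 33 + 0.3 × 20 = 29.1 m, given as about 29 m. With 150 per arm and SD 75 m, power at 29 m is 91.8%, which agrees with "A sample size of 300 patients provides >90% power for a 2-sided test". The sample size is not in dispute.

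**Standard error under each model, complete data.**
- Visit-specific variance: SE = 75 × √(2/150) = 8.66 m.
- Random intercept with homogeneous residuals: SE = √(mean of the three visit variances × 2/150).
- Ratio r = √(mean variance)/75; true alpha = 2 × [1 − Φ(1.96 r)].

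Example with SDs 60/68/75: mean variance = (3600 + 4624 + 5625)/3 = 4616; pooled SD = 67.9 m; SE = 7.85 m; r = 0.906; alpha = 0.076.

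| SD at Months 6/9/12 (m) | Pooled SD (m) | Model SE (m) | r | True alpha |
|---|---|---|---|---|
| 75/75/75 (flat) | 75.0 | 8.66 | 1.000 | 0.050 |
| 68/71/75 | 71.4 | 8.24 | 0.952 | 0.062 |
| 60/68/75 | 67.9 | 7.85 | 0.906 | 0.076 |
| 53/65/75 (variance proportional to time) | 65.0 | 7.50 | 0.866 | 0.090 |
| 37.5/56/75 (SD proportional to time) | 58.3 | 6.73 | 0.777 | 0.128 |
| 85/80/75 (falling) | 80.1 | 9.25 | 1.068 | 0.036 |

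**Check by simulation.** A random-intercept model with treatment-by-visit means was fitted by REML to 300 simulated patients, 1500 runs per scenario. Assumed correlations were 0.7 for adjacent visits and 0.6 between Months 6 and 12, with either no loss or 15% monotone loss at random by Month 12. The Monte Carlo error near 0.05 is √(0.05 × 0.95/1500) ≈ 0.006.

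| Scenario | Type I error, no loss | Type I error, 15% loss |
|---|---|---|
| Flat | 0.045 | 0.047 |
| 68/71/75 | 0.055 | 0.060 |
| 60/68/75 | 0.070 | 0.076 |
| Variance proportional to time | 0.086 | 0.093 |
| SD proportional to time | 0.129 | 0.121 |
| Falling | 0.037 | 0.037 |

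The simulation agrees with the formula. With variance proportional to time and 15% loss, the estimate's actual SE was 8.88 m against a model SE of 7.74 m.

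**Can the SAP put this right within the protocol's wording?** Only partly. Visit-specific residual variances can be added to a random patient intercept. A fully unstructured residual matrix cannot sensibly be: over three visits it already has 3 variances and 3 covariances free, so a random-intercept variance is absorbed into it and is not identifiable. The unstructured MMRM means removing the term the protocol states.

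**The case against.** The strongest reply is that the protocol does not say the residuals are independent or homogeneous. It says MMRM, a label often used for a model with unstructured covariance, and it names a patient effect. Covariance structure, estimation method, degrees of freedom and convergence rules are ordinary SAP content, and section 7.2 calls its own text a brief summary. This stands in part. A reader might infer that the protocol imposes one common variance, but the words do not go that far: homogeneous residuals are implied by a literal reading, not stated. It does not dispose of the point, because the protocol is not silent. It names one within-patient term, the SAP must follow the protocol's principal features, and the usual unstructured model would depart from that term.

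The second reply is that the harm depends on SDs that nobody has supplied. That stands fully. A reader might infer that the Month 12 interval is too narrow and that Type I error exceeds 5%. The documents support neither as a fact: with flat SDs there is no error, and with falling SDs the test errs the other way.

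A reader might also infer a contradiction with the strong Type I error control claimed in section 7.2.5. There is none. That sentence concerns multiplicity across the primary and secondary endpoints, and the fixed sequence it describes is internally consistent. A variance misspecification within one test is a different matter.

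For KCCQ-OS, the text promises a similar model, not an identical covariance, and gives no SDs, so no size can be put on the effect there.

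**Conclusion.** The point holds as a conditional one. The only within-patient term the protocol names, taken literally with ordinary residuals, is compound symmetry, and the Month 12 contrast would then rest on a variance pooled over three visits. If the SD rises to 75 m by Month 12, the standard error is about 5% to 22% too small (r from 0.952 to 0.777) and two-sided alpha about 0.06 to 0.13. The upper end needs the Month 6 SD to be half the Month 12 SD. Flat SDs give 0.05; falling SDs give about 0.036.

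These sizes rest on assumed Month 6 and 9 SDs, homogeneous independent residuals and a large-sample normal approximation. The SAP and the Amendment 2 body could not be checked. The case for changing the wording does not depend on which variance pattern is true: an unstructured covariance handles all of them.

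**What to change.** In section 7.2.5.1 and the synopsis, keep the fixed terms and replace the clause making patient a random effect with: *with an unstructured within-patient covariance across Months 6, 9 and 12 (REML, Kenward-Roger degrees of freedom), with a prespecified fallback if it does not converge*. State in section 7.2.5.2 that KCCQ-OS uses the same structure. First confirm that the Amendment 2 body still carries the present wording.

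The cost is one sentence in each place and six covariance parameters instead of two, which is negligible with 300 patients. With complete data and SD 75 m at Month 12, the standard error is 8.66 m, alpha 0.05 and power at 29 m 91.8%, so the planned sample size is unaffected.
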